Medications for glucose control (insulin, metformin, gliptins, GLP-1 agonists, sulfonylureas, sodium glucose co-transporter inhibitors), antihypertensives, hormone replacement therapy, antidepressants, anticoagulants, or statins, will be considered during recruitment, analyses (e.g., using covariate analysis) and interpretation.

Exclusion criteria for hypocaloric low-fructose diet intervention (part 3):

- 1) Habitual diet containing low amount of sugars < 5% of total energy intake
- 2) Recent CVD event (stroke, heart failure hospitalization, revascularization or acute coronary event in the last 12 months), abnormal thyroid tests or chronic liver disease, stage IV renal disease (GFR <30) and hyperparathyroidism.
- 3) Use of azathioprine
- 4) Active cancer
- 5) Autoimmune diseases
- 6) Excessive alcohol consumption (>14 drinks/week for men, >7 drinks/week for women)
- 7) Current tobacco use
- 8) Bodyweight change $\geq 10\%$ within the last 6 months
- 9) History of gout or uncontrolled hypertension
- 10) Pregnancy or lactation in women (or women not using contraceptives)

Medications for glucose control (insulin, metformin, gliptins, GLP-1 agonists, sulfonylureas, sodium glucose co-transporter inhibitors), antihypertensives, hormone replacement therapy, antidepressants, anticoagulants, or statins, will be considered during recruitment, analyses (e.g., using covariate analysis) and interpretation.

VI. NUMBER OF SUBJECTS

Sample size calculations are based primarily on satisfying the requirements of Aim 2, i.e. to show that XO inhibition and fructose restriction reduce PWV, and that these interventions are more effective in women than in men. Calculations are based on the paired *t*-test for pre- to post-treatment change, and independent *t*-tests for comparisons between treatment arms. In both cases, we assume an alpha of .05 and a two-sided alternative.

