The sample size calculations shown in **Table 2** are derived from the literature as follows: De Angelis *et al* have shown that in men, T2D does not increase PWV in age- and BMI-matched men without T2D ³². By contrast, in women, T2D significantly increases PWV compared to women without T2D and importantly, compared to men with T2D. Any reduction in PWV represents a significant reduction in cardiovascular risk ⁷. However, with 6 months of allopurinol treatment, we have chosen a sample size to be able to detect a reduction in PWV of 0.6 m/s, which Ng *et al* showed to be clinically meaningful ⁶⁸. Nine subjects per group (9 men and 9 women) completing the allopurinol arm will allow for 90% power to detect a change of 0.6 m/s and seven subjects/group will allow for 80% power to detect this change **Table 2**. With regard to fructose restriction, our preliminary

Treatments	Power	Alpha	Change PWV	SE of Δ in PWV	# of subjects
Allopurinol	90%	0.05	0.6 m/s	0.4 m/s	9
	80%	0.05	0.6 m/s	0.4 m/s	7
Low-fructose	90%	0.05	0.5 m/s	0.4 m/s	13
	80%	0.05	0.5 m/s	0.4 m/s	10

Table 2

data demonstrate a significant improvement in PWV only in the females. We anticipate that the reduction in PWV with diet may be smaller than that with allopurinol. We would need 13 subjects/group to detect a 0.5 reduction in PWV with 90% power; 10/group would give 80% power. Further, as we do not expect changes in the PWV during 6 month of follow up in the placebo group and to accommodate variability in response and potential dropout, we will include 40 subjects in the low-fructose intervention, 40 subjects in the allopurinol cohort and 20 in the placebo group (half men and half women for all the cohorts). Further and based in our previous weight loss/dietary intervention⁶⁹, we have chosen a sample size to be able to detect a reduction in PWV of 0.6 m/s of 20 diabetic males and 20 diabetic females.

VII. STUDY PROCEDURES/ DESIGN/TREATMENT PLAN

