Sources will include the subject's medical history, physical exam, screening laboratory tests (CMP, lipid panel, uric acid, insulin, A1c), dual-energy X-ray absorptiometry (DEXA, total and regional fat mass and fat-free mass), blood tests, aortic PWV, cIMT, brachial and popliteal artery flow-mediated dilation (FMD), OGTT with femoral artery blood flow results, CEU-insulin clamp results, and food intake. Demographic data (plus other related data: emergency contact person, pregnancy status), blood pressure, and anthropometrics will be measured (height, weight, waist circumference). Each subject in parts 1 or 3 (diet interventions) of the study, will donate up to 410 ml of blood (screening through final visit) which will occur over a period of up to 6 months. For Part 2 drug treatment, each subject will donate up to 470mls of whole blood (screening through final visit) which will occur over a period of 6 months.

K. Blinding and subject safety

All of [name] s laboratory staff will be blinded as they perform biochemical assays on serum from the drug/placebo study, the isocaloric fructose-restriction study, or the hypocaloric fructose-restriction study. [name] and the assistant performing vascular measurements will be blinded. For the drug study, safety officer cardiologist [name], rheumatologist [name] and [name] will review screening values to determine subject eligibility. Once the subject is randomized, the subjects themselves, investigators, and all CRC staff working with the subjects will be blinded to treatment group (allopurinol or placebo). During the fructose-restriction studies, the CRC staff and the study dietitian nutritionist will not be blinded because subjects serve as their own control and all subjects will be changing their diets (cannot blind to this treatment). No adverse effects of fructose restriction are anticipated but should subjects exhibit changes in their health status across any system related or unrelated to the dietary treatment, [name] or [name] will be consulted for advice.

VIII. Potential Risks/Adverse Events

A. Potential Risks to Human Subjects

The following are the potential risks:

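### Isocaloric diet arm (Part 1): no diet v placebo comparison is named, so a 6-month drift in pulse wave velocity shared by the arms would be read as a diet effect in the paired test

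*Combined protocol and SAP*

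**What the plan says.** Section VII.K, explaining why clinic staff and the dietitian are not blinded in the diet studies, states that "subjects serve as their own control and all subjects will be changing their diets".

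Section VI names two kinds of test: "Calculations are based on the paired *t*-test for pre- to post-treatment change, and independent *t*-tests for comparisons between treatment arms". It adds that "we assume an alpha of .05 and a two-sided alternative". It does not say which arms the independent tests compare. Aim 2 in section I.B sets xanthine oxidase inhibition against dietary reduction of uric acid. No section names diet against placebo.

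For the isocaloric diet, section VI says: "We would need 13 subjects/group to detect a 0.5 reduction in PWV with 90% power; 10/group would give 80% power". Table 2 gives the variability as 0.4 m/s in a column headed "SE of Δ in PWV".

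The numbers are then raised partly on the ground that "as we do not expect changes in the PWV during 6 month of follow up in the placebo group", and "we will include 40 subjects in the low-fructose intervention, 40 subjects in the allopurinol cohort and 20 in the placebo group", each group half men and half women.

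Four further points matter here:
- Section V gives Parts 1 and 2 one exclusion list and Part 3 a separate one.
- The Figure 6 legend puts interim and final visits at months 3 and 6 in every arm.
- Section VII describes randomisation only between allopurinol and placebo.
- Section VII.A describes entry to Part 1 or Part 2 as following a discussion with the subject.

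**The concern.** A paired test of "for pre- to post-treatment change" estimates the diet effect only if PWV would have stayed level over six months without the diet. Ageing, season, changes in blood pressure or glucose-lowering drugs, and the effect of being in a study can all move PWV. The paired test cannot separate these from the diet. A shared fall would be credited to fructose restriction, and a shared rise would hide a real benefit.

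The plan treats this risk by assumption. Yet it recruits 20 placebo subjects whose PWV change over the same interval would show whether the assumption holds. If that information is left out of the Part 1 assessment, the before-after change cannot support the claim in the background section that the design will accurately assess the effect of lowering dietary fructose on arterial stiffness.

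**Working it through.** **1. Reproduce Table 2.** Inputs are in section VI and Table 2: two-sided alpha 0.05, spread 0.4 m/s, differences of 0.6 m/s (allopurinol) and 0.5 m/s (diet). The two-group normal formula is n per group = 2 × SD² × (1.96 + z)² / difference², with z = 1.2816 for 90% power and 0.8416 for 80%.

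| Row | Two-group formula, SD 0.4 | Table 2 | Paired t-test, SD 0.4 |
|---|---|---|---|
| 0.6 m/s, 90% | 9.34 | 9 | 7 |
| 0.6 m/s, 80% | 6.98 | 7 | 6 |
| 0.5 m/s, 90% | 13.45 | 13 | 9 |
| 0.5 m/s, 80% | 10.05 | 10 | 8 |

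For example, 2 × 0.16 × (1.96 + 1.2816)² / 0.25 = 13.45. Rounded to the nearest integer, the two-group formula returns all four entries; the paired test does not. So the 0.4 m/s behaves as an SD of the change, despite the column heading, and it is read that way below. The table also fits a comparison of two groups better than an own-control test.

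**2. Paired test when the diet does nothing but PWV drifts.** The documents give no drift figure, so the sizes are assumptions. The noncentrality is (drift / SD) × √n, and the probability comes from the noncentral t distribution with n − 1 degrees of freedom. For drift 0.2, SD 0.4 and n=20 it is 0.5 × √20 = 2.24, against a critical value of 2.09.

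| Assumed drift | SD of change | n=20 (one sex) | n=40 (pooled) |
|---|---|---|---|
| 0.2 m/s | 0.4 | 56% | 87% |
| 0.1 m/s | 0.4 | 19% | 34% |
| 0.2 m/s | 0.8 | 19% | 34% |

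The second and third rows agree because the ratio of drift to SD is the same. The nominal rate is 5%. After the 10% dropout allowed in section III.A, the first row becomes 52% (n=18) and 83% (n=36).

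**3. Can the planned numbers support diet v placebo?** SE = SD × √(1/n₁ + 1/n₂). At SD 0.4 with 40 v 20 this is 0.4 × √(0.025 + 0.05) = 0.11 m/s, against 0.4 / √40 = 0.06 m/s for the paired change. Power for 0.5 m/s (two-sided 0.05, two-sample noncentral t on the change):

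| SD of change | 40 v 20 | 36 v 18 | 20 v 10 | 18 v 9 |
|---|---|---|---|---|
| 0.4 | 99% | 99% | 88% | 84% |
| 0.6 | 85% | 81% | 55% | 50% |
| 0.8 | 61% | 57% | 34% | 31% |

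The SDs of 0.6 and 0.8 are assumptions that show the range. The 36 v 18 and 18 v 9 columns are after 10% dropout.

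**4. Is placebo comparable?** For Part 1, the exclusion list is shared and the main vascular visits match. For Part 3 it is not comparable. Its list omits the exclusions for uric acid below 5.5 mg/dL and for A1C above 10.0, and it takes people who are ineligible for, or decline, Parts 1 and 2. Section VII.A also calls Part 3 a five-month arm, where other sections say six months; these statements must be reconciled.

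**The case against.** The best defence is that between-arm testing is already planned. The sentence in section VI goes on from the paired test to independent t-tests, and Table 2 fits a two-group formula. The own-control phrase explains blinding and is not an analysis rule. All of this stands. A reader might infer that the plan tests the diet only by before-after change, or has decided to leave placebo out. The text supports neither reading. What it shows is that the arms are not named and that the one between-arm aim is drug against diet.

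Some sources of drift are weak or partly handled:
- PWV is measured at screening and again at baseline, which reduces familiarisation effects.
- No entry criterion selects on PWV, so regression to the mean would act only indirectly, through uric acid.
- Vascular assessors are blinded.
- Medications are to be considered in the analyses, for instance as covariates, though the text does not mention changes during the study.

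These points make a large drift less likely, but they do not rule one out.

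The placebo contrast has biases of its own. Subjects are not randomised between Parts 1 and 2. Placebo is blinded and the diet is not. The drug arm has extra safety visits, while the diet arm has provided food and counselling. The contrast removes shared drift but not selection. That is a fair reason to report it beside the paired change and not to insist that it replace it.

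**Conclusion.** The point holds for Part 1. The plan assumes zero drift, has a placebo group that could check this, and names no comparison that would use it. The paired change alone should not be attributed to the diet.

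The size of the problem depends on two unknowns, the drift and the SD of the change. Over the cases shown, the false-positive rate of the paired test runs from 19% to 87%. A reader might take the upper figure as typical, but it needs a drift of 0.2 m/s, SD 0.4 and both sexes pooled, and the documents give no drift at all.

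The planned numbers are adequate for diet v placebo on the plan's own inputs (99% pooled and 84% within sex after dropout). A reader might conclude that they are always enough. They are not at SD 0.8, least of all within sex (31%).

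A reader might also extend the point to both diet arms. Part 3 draws on a different population, so the placebo group is not a like-for-like control for it.

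**What to change.** In section VI, state which arms the independent comparisons cover, and include Part 1 v placebo for 6-month carotid-femoral PWV. Use ANCOVA on baseline PWV, age and sex, give the result pooled and by sex, and label it non-randomised. Report it beside the paired change, and do not attribute the paired change to the diet unless this contrast supports it. Report Part 3 as an uncontrolled before-after result.

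This is a change of analysis wording, with no added subjects or visits. The price is a wider interval than the paired test gives (SE 0.11 against 0.06 m/s pooled at SD 0.4, before covariate adjustment) and possible selection between Parts 1 and 2, which the report should acknowledge.

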Dose escalation scheme: The dose escalation scheme for allopurinol, **Table 1**, is supported by past work^{60, 62}. The doses of drug will be increased according to the scheme presented in **Table 1** until a target dose of 300 mg is reached, while closely monitoring for any adverse effects. Safety visits will be scheduled every 2 weeks during months 1-2 (at weeks 2, 4, 6, and 8) and every 4 weeks during months 3-6 (at weeks 12, 16, 20) to monitor blood chemistries. Subjects may have safety labs repeated at the discretion of the safety officer.

Study window	Visit number	Daily dose	How many days
Day -30	v0, screening		
Day 0	v1, day 1		
Day 1-14	v2, day 14	100 mg daily	X 14 days
Day 15-28	v3, day 28	200 mg daily	X 14 days
Day 29-168	v4, day 42	300 mg daily	X 133-147 days

Table 1

B. Rationale for choosing the drug and dose:

Allopurinol was chosen as it is used clinically for management of gout and hyperuricemia. As mentioned before the dose and the escalation scheme for allopurinol, below, is supported by past work and available literature.^{60, 62}

C. Risks of not treating hyperuricemia in the placebo group:

A 2013 Cochrane review emphasized the lack of sufficient evidence to support the use of urate-lowering therapy to prevent future gout in hyperuricemic, asymptomatic patients⁶³. A need for further clinical trials to test other benefits of lowering SUA was called for⁶⁴ which strongly supports the rationale for the current study.

Given the limited duration of subject participation (6 months), the lack of known risk to the subject for not being treated is balanced by the significant knowledge gained from this study. At the study's end, subjects in the placebo arm will be offered one, no-cost counseling sessions with the dietitian nutritionist, who will have analyzed their ad libitum food intake and body composition. The dietitian nutritionist will make recommendations to these subjects for modifying lifestyle factors to reduce SUA and improve overall health.

D. Risks and safety information

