Phlebotomy: The total blood withdrawn will not exceed 550 mL in any 8 week period. Hematocrit is measured during screening and before the interim and final visits to check that it is within safe limits (**Table 3** and **Table 4**). All subjects will be advised to refrain from donating blood during public blood drives, during their participation in this project.

These activities are associated with a small risk of phlebitis, bruising and minor pain. Antiseptic technique will be used by nurses who are experts in phlebotomy and catheter placement. If phlebitis occurs, it will be treated conservatively with heat and when appropriate, with antibiotics.

Time point	Volume of whole blood (mls)
Screening	60
Baseline visit	145
SUA concentration	10
SUA concentration	10
SUA concentration	10
Interim visit	35
SUA concentration	10
SUA concentration	10
SUA concentration	10
Final metabolic test	170
Total	470

Table 3. Blood volume taken over the study in the allopurinol/placebo arm

Adherence and serum and urine biochemistries: The SUA response to drug treatment and the pill counts will be used to assess adherence to the drug/placebo arms. Some plasma will be frozen for analysis of potential biomarkers of cardiac and arterial (CA) stiffness. Estimated glomerular filtration rate (GFR) is calculated via the Modification of Diet in Renal Disease Study equation, $GFR = 175 \times \text{standardized serum creatinine} - 1.154 \times \text{age} - 0.203 \times 1.212$ [if black] $\times 0.742$ [if female], where GFR is expressed as mL/min/1.73 m² of BSA and creatinine is expressed in mg/dL⁷¹.

Indirect calorimetry: Fasting energy expenditure and substrate oxidation are measured at the beginning of the metabolic test. Calorimetry carries no risk, however, this test may cause discomfort in those who are fearful of confined spaces or claustrophobic. Before the procedure is performed, subjects are allowed to become familiarized with the hood used to collect expired gas.

Aortic pulse wave velocity (cfPWV): This procedure poses no risks.

Carotid artery intima-media thickness (cIMT): This procedure poses no risks.

Brachial artery and popliteal flow-mediated dilation (FMD) with NIRS: This is a measurement of endothelial function. There are no risks associated with this procedure.

Oral glucose tolerance test (OGTT): At screening, subjects will have an oral glucose tolerance test performed. This might cause blood sugar levels to be elevated following the completion of the test.

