Although risks from the *dietary* intervention protocol in our proposal are minimal, the *drug* treatment could pose risk to participants. The data and safety monitoring plan (DSMP) for this trial focuses on close monitoring by the PI and the safety officer.

Frequency of monitoring, including any plans for interim analysis and stopping rules. Monitoring will include enrollment, attrition, efficacy end-points, and adverse events. In addition to monitoring by the PI, study coordinator, and safety officer monitoring, the MU IRB monitors all aspects of the project on an annual basis. The DSMC conducts its reviews on a semiannual basis. The frequency of the structured data review for this study can be summarized in the following table:

Data type	Frequency of review
Subject accrual (adherence to protocol regarding demographics, inclusion/exclusion)	At the end of each recruitment
Adverse event rates (injuries)	semi-annually
Compliance to treatment	semi-annually
Out of range laboratory data	semi-annually
Stopping rules report regarding statistical power implications of dropouts and missing data	semi-annually
IRB review	annually
DSMC review	semi-annually

Table 6

C. Process for Managing and Reporting Adverse Events, Serious Adverse Events and Unanticipated Problems:

Events that meet the three IRB criteria of being: unexpected, related or possibly related to research participation, and suggesting that research places subjects or others at a greater risk of harm than previously known or recognized will be reported to the IRB. Both serious and non-serious adverse events will be reported to the MU School of Medicine Data and Safety Monitoring Committee (DSMC). For reporting to the DSMC, adverse events will be categorized and classified according to Common Terminology Criteria for Adverse Events Scale (CTCAE v3.0). Safety reports will be sent to the safety officer. The PI will be responsible for assembling the data and producing these reports, as well as assuring that all parties obtain copies of these reports.

D. Qualifications and responsibilities of the Safety Officer:

The safety officer for this trial will be [name]/PhD. **[name] is an Assistant Professor in the Division of Cardiology.** In addition to practicing medicine, he is a clinician scientist. As Safety Officer, [name] will review eligibility criteria with [name], and will be unblinded as to treatment assignment. He will review all reports sent by the study coordinator to determine whether

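### The drug/placebo study blinds investigators and CRC staff but judges adherence by serum uric acid response and does not limit who sees on-treatment values

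*Combined protocol and SAP*

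**What the plan says.** Section VII.K sets the blind for the drug study: once a subject is randomised, "the subjects themselves, investigators, and all CRC staff working with the subjects will be blinded to treatment group". It makes no exception for the PI. Section XII.D names the safety officer as the person who knows treatment assignment. Section VII.K also blinds the assay laboratory staff and those who take the vascular measurements.

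Section VIII.A, under adherence and biochemistries, says: "The SUA response to drug treatment and the pill counts will be used to assess adherence to the drug/placebo arms". Table 3, headed "Blood volume taken over the study in the allopurinol/placebo arm", lists six stand-alone SUA draws that do not appear in the diet arms' Table 4. Section II.A adds safety visits every two weeks in months 1-2 and then "every 4 weeks during months 3-6 (at weeks 12, 16, 20) to monitor blood chemistries".

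On oversight, section XII.B says: "Monitoring will include enrollment, attrition, efficacy end-points, and adverse events". The text goes on: "In addition to monitoring by the PI, study coordinator, and safety officer monitoring", with the IRB reviewing annually and the DSMC semi-annually. Table 6 lists compliance and out-of-range laboratory data for semi-annual review, without naming who compiles them, and has no row for efficacy. Section XII.D lets the safety officer comment on whether the PI needs to report particular out-of-range results, which suggests that the PI holds some laboratory data.

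No section withholds on-treatment SUA from the PI, the other investigators, the coordinator or CRC staff. Section VIII.E says in general terms that the analysis will be suitably blinded, but sets no rule on access to SUA.

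**The concern.** Section I.B gives lowering SUA as the goal of Part 2, so SUA is the direct marker of the drug's action. A plan that blinds investigators and then assesses adherence on that marker needs a rule for who sees it, and there is none.

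The adherence rule also fails on its own terms. It is meant to cover both arms, but a placebo subject who takes every capsule has no drug-induced fall in SUA. A reader who does not know the arm cannot tell that subject from a non-adherent allopurinol subject. A reader who does know the arm is not blinded. This holds whatever the size of the SUA effect.

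At stake is how far the blind protects what investigators and CRC staff do between randomisation and database lock: contact with subjects, decisions about continued participation, and data handling. With 20 placebo subjects, a few decisions made differently by arm could matter.

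**Working it through.** The plan states no figure on this point to reproduce. The check has two parts.

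**1. Tracing the data flow.**

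- Marker collected: the Table 3 rows sum to 60 + 145 + 3×10 + 35 + 3×10 + 170 = 470 mL, the stated total. This confirms six separate SUA draws. Section VII.F also lists uric acid among the fasting blood measurements.
- Reference value available: section V excludes SUA below 5.5 mg/dL from Parts 1 and 2, so a screening SUA exists for every subject. Anyone who sees that value and a later one can form a change.
- Use: section VIII.A applies SUA response to both arms.
- Access: section XII.B puts the PI and coordinator among those who monitor. No section restricts SUA.

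**2. How informative is one SUA change?** The documents give neither the expected fall nor its SD, so both are assumptions: mean fall δ = 1.0 to 2.5 mg/dL on allopurinol, zero on placebo, and SD of change σ = 0.8 to 1.2 mg/dL in each arm, with normal distributions. Section VII gives the allocation as 40:20, so the prior probability of allopurinol is 40/60 = 0.667. Calling every subject allopurinol is therefore right 66.7% of the time, and that is the benchmark.

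Let D = δ/σ. The best cut on the standardised fall is c = D/2 − ln(2)/D, where 2 is the prior odds. The proportion classified correctly is (2/3)·Φ(D − c) + (1/3)·Φ(c).

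- Least informative corner, δ = 1.0 and σ = 1.2: D = 0.833; c = 0.417 − 0.832 = −0.415; Φ(1.248) = 0.894; Φ(−0.415) = 0.339. Correct = 0.667×0.894 + 0.333×0.339 = 0.709.
- Middle, δ = 1.5 and σ = 1.0: D = 1.5; c = 0.288; Φ(1.212) = 0.887; Φ(0.288) = 0.613. Correct = 0.796.
- Most informative corner, δ = 2.5 and σ = 0.8: D = 3.125; c = 1.563 − 0.222 = 1.341; Φ(1.784) = 0.963; Φ(1.341) = 0.910. Correct = 0.667×0.963 + 0.333×0.910 = 0.945.

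So the range is about 71% to 95%, or roughly 4 to 28 percentage points above guessing. The share of placebo subjects correctly picked out runs from 34% to 91%; guessing allopurinol for everyone picks out none. If the true difference were only 0.5 mg/dL, with σ of 0.6 to 1.0, the same formula gives 68-71%, little better than guessing. Repeated values could add information, but that was not computed, and the early draws fall during dose escalation.

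**The case against.** The strongest reply is that the protocol is silent on access to SUA and does not plan to disclose it. Several tempting readings go further than the text.

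- A reader might infer that the blinded PI compiles SUA-based compliance reports, because section XII.C says "The PI will be responsible for assembling the data and producing these reports". That sentence follows directly on the adverse-event and safety reports, and in context refers to those. Section XII.D also has the safety officer reviewing reports sent by the coordinator. The documents do not say who compiles compliance.
- A reader might infer that monitoring efficacy end-points reveals assignment. Values of cfPWV not split by arm identify nobody, and no section says that they are split.
- A reader might infer that SUA reveals each subject's arm. Identification is only probabilistic, and at the low end of the assumed range the gain over guessing is about 4 points.
- A reader might infer that repeat laboratory tests, drug stopping and counselling are all exposed. Repeat safety tests are at the unblinded safety officer's discretion (section II.A). Section VIII.D bases stopping the drug on safety criteria or that officer's discretion. Dietitian counselling in Part 2 comes after the final visit (section VII.D).

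In addition, cfPWV is a device measurement taken by blinded operators, and the assay staff are blinded.

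All of this stands, and it narrows the point. It does not answer two things: SUA response is a stated adherence measure that cannot work for placebo, and nothing keeps on-treatment SUA from the people the protocol declares blinded.

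**Conclusion.** The concern holds as a modest one. The protocol blinds investigators and CRC staff, uses the drug's direct marker to judge adherence in both arms, involves the PI and coordinator in monitoring that includes efficacy end-points, and sets no limit on who sees on-treatment SUA. The failure of SUA as a measure of placebo adherence needs no numerical assumption. The risk to the blind does: under the assumed falls and SDs, one value classifies about 71-95% of subjects correctly against 66.7% by guessing, and the gain nearly disappears if the SUA separation is about 0.5 mg/dL.

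The documents do not show that the blind will be broken, or that cfPWV readings would be biased. The remaining exposure is in subject contact, participation decisions and data handling by investigators and CRC staff. This is a cheap improvement rather than a flaw that threatens the trial.

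**What to change.** Make three wording changes.

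1. In sections VII.K and VIII.A, state that SUA results after randomisation, including those from the interim and final visits, go only to the already-unblinded safety officer and the DSMC until database lock. Reports that the PI or coordinator assembles or reviews, including any on out-of-range laboratory data, should leave SUA out.
2. In section VIII.A, state that adherence is assessed under the blind by pill count in both arms, and that SUA response is kept for analysis after unblinding.
3. In section XII.B, state that efficacy end-points seen by the PI or coordinator during the trial are pooled over arms, or remove them from ongoing monitoring. Table 6 schedules no efficacy review, so removal would leave that table unchanged.

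The cost is a laboratory reporting instruction and a few sentences, with no new visits, samples or staff. The downside is that blinded staff cannot use SUA to prompt adherence during the trial.
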